##### 52-week Treatment Period Analysis

For the continuous exploratory efficacy variables, including hs-CRP, fecal calprotectin, and IBDQ Score, summary statistics for baseline value, observed values and changes from baseline at scheduled visits including re-allocated EOT visits (see Section 2.3) up to Week 52 visit will be provided for each treatment group.

Line plots showing mean values ( $\pm$  SE) and mean changes from baseline ( $\pm$  SE) at each of the scheduled visits up to Week 52 visit will also be presented by treatment groups.

#### 4.8.3.3. Time to Events Exploratory Efficacy Endpoint

Time to symptomatic response (see Table 2 for definition) by Week 12 will be analyzed using Cox regression model stratified by randomization stratification factors.

Time to symptomatic response is calculated as the number of days from the randomization date to the earliest visit date recorded in the eCRF page when a participant achieved symptomatic response.

If a participant didn't achieve symptomatic response at any visits by week 12 visit, he/she will be censored as follows:

- Censored at the reference date for calculating stool frequency and rectal bleeding subscores at Week 12 visit (see the determination of reference date in Section 6.1) if he/she completed the 12-week Induction Period.
- Censored at the reference date for calculating stool frequency and rectal bleeding subscores at the last visit (include EOT visit but exclude safety follow-up visit) (see the determination of reference date in Section 6.1) if he/she discontinued treatment during the Induction Treatment period.

The hazard ratios for MORF-057 versus placebo will be provided along with the 95% CIs. The Kaplan-Meier plot will be provided.

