## 1.2. Study Design

This study is a randomized, double-blind, placebo controlled, multicenter, Phase 2b study to evaluate the efficacy and safety of 3 active dose regimens of MORF-057 (as capsule, P.O.) versus matching placebo in study participants with moderately to severely active UC.

Approximately 280 participants will be randomized into the treatment groups in a 1:1:1:1 ratio (i.e., 70 participants per group). The study will enroll participants who are advanced therapy naïve (i.e., have no previous exposure to an advanced therapy treatment for UC) and advanced therapy experienced (excluding vedolizumab), with at least 30% but no more than 40% of advanced therapy experienced participants. Randomization stratification factors will include baseline MES (<3 vs 3) and previous use of advanced therapy treatment (advanced therapy naïve vs advanced therapy experienced). All participants will be enrolled from approximately 150 centers worldwide. For this study, moderately to severely active UC will be defined as having an mMCS of 5 to 9 (inclusive), with an MES  $\geq 2$  (confirmed by central reader).

The main part of this Phase 2b study will consist of a Screening Period (up to 6 weeks, consisting of Stage 1 and Stage 2 testing), a Treatment Period (52 weeks, including a 12-week Induction Period and a 40-week Maintenance Period), and a Safety Follow up (SFU) Period (4 weeks).

During the main part of this study, there will be approximately 11 scheduled study visits: Screening Visit(s) (Visit 1 at Weeks 6 to 1), multiple Treatment Visits (Visits 2-10 at Weeks 0, 2, 6, 12, 18, 24, 32, 42, and 52 [End of Treatment (EOT)]), and an SFU Visit (visit to occur 4 weeks after the last dose of study drug is received, which will be at Week 56 if the full Treatment Period is completed or earlier if treatment is discontinued early). Study Day 1 represents the first day of the Treatment Period (i.e., when the participant will receive the first dose of study drug).

All participants who complete the 52-week Treatment Period will have the opportunity to continue their treatment in a 52-week Maintenance Extension Period.

During the optional Maintenance Extension, there will be 5 scheduled visits: 4 Treatment Visits (Visits 11-14 at Weeks 65, 78, 91, and 104 [EOT]) and an SFU Visit (visit to occur 4 weeks after the last dose of study drug is received, which will be at Week 108 if the full Maintenance Extension is completed or earlier if treatment is discontinued early).

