### 1.4. Randomization and Blinding

#### 1.4.1. Randomization

An interactive response technology (IRT) will be used to centrally randomize all participants into 1 of the 4 treatment groups (see [Table 3](#) for dosing regimens). The randomization code will be maintained by the IRT provider. Randomization will be stratified by baseline MES (<3 vs 3) and previous use of advanced therapy treatment (advanced therapy naïve vs advanced therapy experienced). Participants

Morphic Therapeutic, Inc.  
Study Number: MORF-057-202

Statistical Analysis Plan  
Version 1.0, 16SEP2024

initially randomized into the placebo group will be switched to an active MORF 057 regimen (200 mg Q.D. E) after they complete the Induction Period and the scheduled assessments at Week 12 (including endoscopy).

Study treatment will be dispensed at the study visits as summarized in the Schedule of Activities (SoA) in Section 1.2 of the study protocol.

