## 6. APPENDICES

### 6.1. Calculation of Stool Frequency and Rectal Bleeding Subscores

Stool frequency and rectal bleeding subscores at baseline and post-baseline visits will be calculated based on a reference date determined as follows:

- For baseline, the reference date is the randomization date.
- For post-baseline visits, the reference date is:
  - The earliest of the visit date recorded on eCRF form, the start date of bowel preparation (if performed), or the date of endoscopy procedure, if the endoscopy procedure is performed at the visit.
  - The visit date recorded on the eCRF If no endoscopy procedure is performed at the visit.

The calculation of stool frequency and rectal bleeding subscores will use the 3 most recent consecutive days of completed diary entries (both stool frequency and rectal bleeding data must be non-missing on the same day) within the past 7 days from the reference date. If 3 consecutive days of completed diary entries are not available, then use the 4 most recent nonconsecutive days of completed diary entries within the 7-day period prior to the reference date. If there are fewer than 3 consecutive days or 4 nonconsecutive days of completed diary entries available, then the subscores are set to missing.

In the calculations of stool frequency and rectal bleeding subscores at baseline, diaries collected on the following days within the 7-day period from the reference date will be excluded:

- Days of bowel preparation
- The day of endoscopy + 2 days

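### Time to symptomatic response dates events at the visit but censors non-responders at a date that can be earlier, which inflates the last part of the Kaplan-Meier curve

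*SAP*

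**What the plan says.** Section 4.8.3.3 plans a Cox model stratified by the randomization factors, hazard ratios with 95% CIs, and a Kaplan-Meier plot. It uses two dating rules:

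- **Event.** Time runs from randomization "to the earliest visit date recorded in the eCRF page when a participant achieved symptomatic response".
- **Censoring, induction completed without response.** "Censored at the reference date for calculating stool frequency and rectal bleeding subscores at Week 12 visit".
- **Censoring, treatment stopped during induction.** "Censored at the reference date for calculating stool frequency and rectal bleeding subscores at the last visit", where the EOT visit counts and the safety follow-up visit does not.

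Section 6.1 defines the reference date. If endoscopy is done at the visit, it is "The earliest of the visit date recorded on eCRF form, the start date of bowel preparation (if performed), or the date of endoscopy procedure". Otherwise it is the eCRF visit date. Section 1.4.1 counts endoscopy among the Week 12 assessments. Section 1.2 places the induction visits at Weeks 0, 2, 6 and 12.

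Section 1.6 adds time to symptomatic remission by Week 12. Section 4.8.3.4 refers the analysis of symptomatic remission to the proportion methods of Section 4.8.3.1, so the SAP gives this second time-to-event variable no dating rule of its own.

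**The concern.** Take two participants with the same Week 12 calendar: preparation begins the day before the recorded visit, and one responds while the other does not. Section 6.1 derives both outcomes from diary days before the same reference date. Section 4.8.3.3 then gives the responder an event on the visit day and censors the non-responder a day earlier. Their follow-up times differ only because their outcomes differ.

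Both planned outputs assume that censoring carries no information about the outcome. Here a participant already known not to have responded can drop out of the denominator just before the Week 12 responses are counted. Compared with dating everyone at the visit, this can only shrink the Week 12 risk set, so the curve can only move up. A reader who takes the right-hand end of the plot as cumulative response by Week 12 would be misled. An EOT visit with endoscopy has the same mismatch.

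**Working it through.** The SAP gives no figure for this endpoint, so there is none to reproduce. The check compares the plan's dates with consistent dates.

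**Inputs from the SAP.** 70 per arm (Section 1.3); visits at Weeks 2, 6 and 12 (Section 1.2); the dating rules above. Table 6 lists endoscopic endpoints in induction only at Week 12. With no endoscopy at Weeks 2 and 6, the two dates coincide there.

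**Assumed, not in the SAP.** New responders at Weeks 2/6/12 of 30/20/12% active and 20/15/10% placebo; no dropout; lag from reference date to visit of 0 to 2 days; visits on schedule or scattered with SD 2–3 days.

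**Step 1: visits on schedule, by hand, per 100 participants.** The Kaplan-Meier response is 1 − S, where S = (1 − d₂/n₂)(1 − d₆/n₆)(1 − d₁₂/n₁₂).

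Placebo has 20, 15 and 10 responders and 55 non-responders. After Week 6, S = 0.80 × 65/80 = 0.65.

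- No lag: 65 at risk at Week 12. S = 0.65 × 55/65 = 0.55, so response is 45%, the observed proportion.
- Half lagged by one day: 27.5 non-responders are already censored, leaving 37.5 at risk. S = 0.65 × 27.5/37.5 = 0.477, so response is 52.3% (about 53% on average in simulation).
- All lagged: 10 at risk and 10 events. S = 0, so response is 100%.

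Active has 30, 20 and 12 responders and 38 non-responders. After Week 6, S = 0.70 × 50/70 = 0.50.

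- No lag: S = 0.50 × 38/50 = 0.38, so response is 62%.
- Half lagged: S = 0.50 × 19/31 = 0.306, so response is 69.4%.
- All lagged: 100%.

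**Step 2: scattered visits, by simulation, 70 per arm, same rates.**

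| Setting | Placebo KM at Week 12, plan dates | One common date | Nominal visit time |
|---|---|---|---|
| On schedule, half lagged 1 day | about 53% | 45% | 45% |
| SD 2–3 days, lag 1–2 days | about 72–86% | about 63–64% | 45% |
| On schedule, all lagged | 100% | 45% | 45% |

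In the middle row the date mismatch adds between 72 − 64 = 8 and 86 − 63 = 23 points. A further 18–19 points (63–64 against 45) come from applying a continuous-time curve to scattered visit dates, whichever date is used.

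**Step 3: hazard ratio.** On schedule with all participants lagged, it falls from about 1.64 to 1.49. With scatter, plan dates against one common date give, for example, 1.56 against 1.57 and 1.57 against 1.61.

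**Step 4: other assumed rates** (20/20/17% active, 13/13/10% placebo; observed about 57% and 36%). Final KM values, active / placebo:

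- On schedule, half lagged one day: 66% / 44%.
- On schedule, mixed lags of 0–3 days with 80% of participants lagged: 80% / 59%. The hazard ratio is 1.59 against 1.74 with a common visit date.
- Visits scattered ±3 days, all lagged one day: 95% / 82%, against 73% / 48% with a common visit date.
- Visits scattered ±3 to ±5 days, lags of 1–3 days: the hazard ratio is about 1.64–1.78, against about 1.77–1.82 with a common date.

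**The case against.** Several points count against a strong version of this concern.

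- **The lag may be zero.** Section 6.1 takes the earliest of three dates, so the reference date falls on or before the visit date. The SAP does not say how often preparation or endoscopy precedes the recorded visit. If that never happens, nothing goes wrong. This stands, and it is why every size given here is conditional. Still, a rule that takes the earliest of three dates provides for them to differ.
- **A reader might infer that the curve reaches 100% in both arms.** That needs every visit on its scheduled day and every participant lagged. It shows the mechanism at its limit and is not a forecast.
- **A reader might infer that the hazard ratio is generally pulled toward 1.** The calculations do not support this. The pull is clear only when visits sit on schedule and all or most participants are lagged. With half lagged, or with scattered visits and lags of 1–2 days, the ratio hardly changes. With equal arms it stays at 1.00, with no excess of false positives.
- **Not all of the inflation comes from the mismatch.** With scattered visits, a common date still leaves the curve well above the observed proportion. This stands and bears on the choice of fix.
- **The stakes are limited.** Section 4.8.6 keeps exploratory endpoints outside the hierarchy. Section 4.8.3.1 already reports symptomatic response at each visit to Week 12, by non-responder imputation and as observed, so correct proportions will appear beside the plot.

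None of these points justifies two dating rules chosen by outcome, and no other section corrects it.

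**Conclusion.** The concern holds in a limited form. Section 4.8.3.3 dates events and censorings by different rules. At a visit with endoscopy (Week 12, or EOT), the censoring date is never later than the event date would have been. Whenever preparation or endoscopy precedes the recorded visit, known non-responders leave the risk set too soon and the last part of the Kaplan-Meier curve is too high.

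The direction follows from the text. The size does not, because the SAP gives neither lags nor visit scatter. Under the first set of assumed rates, the placebo curve is raised by about 8 points with half the participants lagged one day and visits on schedule (53 against 45), and by roughly 8 to 23 points with scattered visits and lags of 1–2 days. The hazard ratio is little affected in those settings. A reader might also infer a threat to the trial's main conclusion. There is none: the primary and secondary tests do not use these times.

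**What to change.** Put events and censorings on one time scale in Section 4.8.3.3: nominal visit time (Weeks 2, 6 and 12). State that a censoring tied with events at a visit stays in the risk set for those events, and name an exact or discrete method for ties in the stratified Cox model. With nominal times and no dropout, the curve ends at the observed proportion whatever the scatter of visits (45% placebo in the first example).

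Using the same calendar date for both is the lesser repair. It removes the mismatch but leaves the inflation from visit scatter (63–64% against 45%). Using the reference date for both also leaves some inflation when lags differ between participants: with mixed lags and visits on schedule, the second set of rates gives 69% / 46% against 57% / 36%.

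Apply the same rule to the second censoring bullet, and state it for time to symptomatic remission. The cost is a few lines of SAP text and one derivation, before database lock. No new data are needed and the testing hierarchy is unchanged.

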#### 4.8.3.4. Additional Exploratory Efficacy Analysis

Additional exploratory analysis will be performed for change from baseline to Week 12 in the mMCS score by using an analysis of covariance (ANCOVA) model with treatment and randomization stratification factors as factors and baseline values as a covariate. Any participant who was randomized under the wrong stratum by mistakes will be analyzed according to the actual stratum the participant belongs to. The least-squares means and standard errors with 95% CIs for both changes from baseline in each treatment group and differences between MORF-057 and placebo groups will be provided. P-values will also be calculated for the exploratory use. Participants who do not have the baseline value or the value at Week 12 will be excluded from the analysis. The change from baseline to Week 12 in the mMCS score will also be summarized descriptively for each treatment group by previous use of advanced therapy for UC (naïve vs experienced), by baseline MES score (<3 vs 3), and by baseline mMCS score ( $\leq 7$  or  $> 7$ ).

Summary statistics (mean and SD) for baseline value, observed values and changes from baseline at scheduled visits including re-allocated EOT visit (see Section 2.3) will be provided by treatment groups for the following additional continuous exploratory variables on observed cases:

- Stool frequency subscore
- Rectal bleeding subscore
- Partial mMCS

The summaries will be provided both for the overall population and for the subgroups by previous use of advanced therapy for UC (naïve vs experienced) and by baseline MES score (<3 vs 3). The summaries will be provided at each scheduled visit up to Week 12 visit in the Induction Period Analysis, up to Week 52 visit in the 52-week Treatment Period Analysis, and up to Week 104 visit in the 104-week Total Treatment Period Analysis. Line plots showing mean values ( $\pm$  SE) and mean changes from baseline ( $\pm$  SE) at each of the scheduled visits will also be presented by treatment groups, both for the overall population and for the subgroups.

For the histologic variables, i.e., RHI, NI, and continuous Geboes score, descriptive summaries will also be provided by treatment groups for change from baseline at Week 12 in the Induction Period Analysis,

for change from baseline at Week 52 in the 52-week Treatment Period Analysis, and for change from baseline at Week 104 in the 104-week Total Treatment Period Analysis.

Additionally, the proportion and 95% CI will be provided by treatment groups for participants with clinical remission, clinical response, and Corticosteroid-free remission at Week 104.

Symptomatic remission, which is defined as stool frequency subscore = 0 (or = 1 with  $\geq 1$  point decrease from baseline) and rectal bleeding subscore = 0, will be summarized in the same manner as symptomatic response, as described in Section 4.8.3.1.

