Participants who do not enroll into the Maintenance Extension must complete the final SFU Period for the main part of the study, including the Week 56 Visit (4 weeks after receiving the last dose of MORF-057), for a maximum time on study of 62 weeks. Participants who choose to continue in the Maintenance Extension will not complete the SFU Period for the main part of the study; instead, they

Morphic Therapeutic, Inc.  
Study Number: MORF-057-202

Statistical Analysis Plan  
Version 1.0, 16SEP2024

will directly enter the Maintenance Extension and complete a separate SFU Period, including the Week 108 Visit (4 weeks after receiving the last dose of MORF-057), for a maximum time on-study of 114 weeks.

An independent Data and Safety Monitoring Board (DSMB) will review participant safety data and monitor scientific integrity throughout the study. Details related to the DSMB will be clearly delineated in the DSMB Charter.

[figure not shown]
Enrolled participants will be randomized to a treatment group to receive active MORF-057 or placebo. Participants initially randomized into an active MORF-057 treatment group will receive an active treatment (according to study period and group assignment) for the full 52-week Treatment Period. Participants initially randomized into the placebo group will be switched to an active MORF-057 regimen (200 mg once a day – evening [Q.D.E]) after they complete the Induction Period and the Week 12 assessments. After participants complete the full 52-week Treatment Period, they will have the option to enter an additional 52-week Maintenance Extension Period. All participants who choose to continue in the Maintenance Extension will continue receiving the same MORF-057 regimen they had during the Maintenance Period for up to an additional 52 weeks. The dosing regimens for the 4 treatment groups during the study are shown below.

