### 1.3. Sample Size and Power

The sample size was determined based on the primary endpoint of clinical remission at Week 12 by using the Chi-Squared Test to compare two proportions. A sample size of 70 participants per group (giving a total of 280) will provide 80% power to detect a difference of 15% in the clinical remission rate between MORF-057 and placebo, based on the use of a two-sided test at the alpha=0.10 level of significance. The calculation is based upon an assumed placebo remission rate of 7%.

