### **52-week Treatment Period Analysis and 104-week Total Treatment Period Analysis**

All proportion-based exploratory efficacy endpoints at Week 52 and Week 104, as outlined in [Table 6](#), will be summarized descriptively by treatment groups. The proportions, along with their corresponding 95% CIs, will be provided for the overall population, by previous use of advanced therapy for UC (naïve vs experienced), by baseline MES score (<3 vs 3), and by baseline mMCS score ( $\leq 7$  or  $> 7$ ). The denominator for calculating the proportions for each treatment group will be the total number of participants in the FAS within that group, except for the group initially randomized to placebo, which will use the total number of participants continuing to the Maintenance Period as the denominator.

In addition, the proportion of participants with symptomatic response and the proportion of participants with partial MCS response, along with the 95%CI, will be summarized by treatment groups at each

scheduled visit up to Week 52 in the 52-week Treatment Period Analysis and up to Week 104 in the 104-week Total Treatment Period Analysis. The summaries will use the following two approaches:

- All randomized: at each visit, proportions for each treatment group will be calculated using the total number of participants in the FAS within that group as the denominator, except for the group initially randomized to placebo, which will use the number of participants continuing to the Maintenance Period as the denominator. Participants with missing data will be considered as non-responders by using the NRI method. The calculations will include the re-allocated EOT visits (See the re-allocation approach in Section 2.3) at that visit.
- As observed: at each visit, the denominator for calculating the proportions will be the number of participants with non-missing assessment at that visit, without including the re-allocated EOT visits and without using the NRI method.

The above summaries for proportions of participants with symptomatic response and partial MCS response will also be provided for the subgroups by previous use of advanced therapy for UC (naïve vs experienced), and by baseline MES score (<3 vs 3), in both 52-week Treatment Period Analysis and 104-week Total Treatment Period Analysis. Line plots showing the proportion ( $\pm$  95% CI) at each of the scheduled visits will be provided for each treatment group, both for the overall population and for the subgroups.

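### The by-visit means of stool frequency, rectal bleeding and Partial mMCS run to Week 104 on observed cases alone, so outcome-related dropout or Extension refusal could shift the curves with no within-patient change

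*SAP*

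**What the plan says.** Section 4.8.3.4 plans baseline, observed-value and change-from-baseline summaries "for the following additional continuous exploratory variables on observed cases": stool frequency subscore, rectal bleeding subscore and Partial mMCS. They run to Week 12 in the Induction Period Analysis, then "up to Week 52 visit in the 52-week Treatment Period Analysis, and up to Week 104 visit in the 104-week Total Treatment Period Analysis". Means and mean changes are also drawn as line plots, overall and by subgroup. No imputed, model-based or constant-cohort version is named, and section 2.4 makes observed cases without imputation the general default.

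Four other provisions bear on this:

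- **Extension entry (section 1.2).** It is voluntary and open only to Week 52 completers: "they will have the option to enter an additional 52-week Maintenance Extension Period".
- **Early stopping (section 2.3).** An end-of-treatment value can be moved to one neighbouring scheduled visit. It is not carried further.
- **Binary rates (section 4.8.3.1, 52-week and 104-week analyses).** Symptomatic response and Partial MCS response are given two ways at each visit. One uses the FAS denominator with NRI (for the placebo-start group, those continuing to Maintenance). The other is as observed, where "the denominator for calculating the proportions will be the number of participants with non-missing assessment at that visit". Section 4.8.3.4 treats symptomatic remission in the same manner. The text does not say which of the two the proportion plots show.
- **Status (section 4.8).** The Week 52 and Week 104 endpoints are exploratory and summarised descriptively.

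**The concern.** A line of mean change from baseline to Week 104 is naturally read as the course of symptoms on drug. Here each point describes a different set of people: nearly everyone early on, those still observed at Week 52, then only those who chose the Extension and stayed in it. The composition can change abruptly between Week 52 and Week 65 within one plotted line.

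If staying is related to outcome, the mean moves because the membership moves. For these three continuous scores the SAP offers no second analysis beside which the reader could judge that. At stake is the description of durability of effect; no hypothesis test depends on it.

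**Working it through.** **1. The plan's own figure.** The SAP states no dropout, Extension uptake or Week 104 number. Its only design figure is 80% power with 70 per group, 7% against 22%, two-sided alpha 0.10 (section 1.3). With a pooled null variance, SE0 = sqrt(2 x 0.145 x 0.855 / 70) = 0.0595 and SE1 = sqrt((0.07 x 0.93 + 0.22 x 0.78) / 70) = 0.0582. Then (0.15 - 1.645 x 0.0595) / 0.0582 = 0.90, which gives 81.5% power. The stated figure reproduces. It serves here only to supply a group size of 70.

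**2. Illustration, all inputs assumed.** Take 70 participants, 40% responders with a constant change of -3.0 and 60% non-responders with a constant change of -0.5. Nobody changes after Week 12, so the true mean is 0.4 x (-3.0) + 0.6 x (-0.5) = -1.50 at every visit. Let a, b and c be retention to Week 52, Extension entry, and retention from entry to Week 104.

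- Responders observed at Week 104: R = 28 x a x b x c, with the responders' rates
- Non-responders observed: N = 42 x a x b x c, with the non-responders' rates
- Observed mean = (-3.0R - 0.5N) / (R + N)
- As-observed response = R / (R + N)
- NRI response = R / 70

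| Attrition | Responders a, b, c | Non-responders a, b, c | n, Wk 104 | Mean, Wk 52 | Mean, Wk 104 | As observed, Wk 104 | NRI, Wk 104 |
|---|---|---|---|---|---|---|---|
| Equal | .75, .80, .85 | .75, .80, .85 | 35.7 | -1.50 | -1.50 | 40.0% | 20.4% |
| Mild | .85, .90, .90 | .75, .80, .85 | 40.7 | -1.58 | -1.68 | 47.4% | 27.5% |
| Moderate | .90, .95, .90 | .60, .60, .70 | 32.1 | -1.75 | -2.18 | 67.1% | 30.8% |
| Strong | .95, .95, .95 | .40, .50, .60 | 29.0 | -2.03 | -2.57 | 82.6% | 34.3% |
| Reverse | .70, .75, .85 | .80, .85, .85 | 36.8 | -1.42 | -1.35 | 34.0% | 17.9% |

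Moderate row in full: R = 28 x 0.90 x 0.95 x 0.90 = 21.55; N = 42 x 0.60 x 0.60 x 0.70 = 10.58; mean = (-64.64 - 5.29) / 32.13 = -2.18.

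**3. Re-allocated end-of-treatment values.** Section 4.8.3.4 includes them in the means. Suppose dropout is spread evenly over the visit intervals and every dropout's value is moved to the next visit. The moderate Week 104 mean is then -2.14 instead of -2.18. The rule softens the drift only slightly.

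**4. A second set of assumptions.** Take half responders, retention to Week 52 of 85-90% in responders and 45-70% in non-responders, Extension entry of 90% and 60-90%, and later retention of 90% and 70%.

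- Low end: 0.85 x 0.90 x 0.90 = 0.689 against 0.70 x 0.90 x 0.70 = 0.441, so observed response is 0.689 / 1.130 = 61%.
- High end: 0.90 x 0.90 x 0.90 = 0.729 against 0.45 x 0.60 x 0.70 = 0.189, so 0.729 / 0.918 = 79%.

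The true rate is 50% throughout. This set covers only selection against non-responders.

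**5. What the candidate remedies do (moderate row).**

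- Entrants number 25.2 x 0.95 = 23.94 responders and 25.2 x 0.60 = 15.12 non-responders. Their mean is (-71.82 - 7.56) / 39.06 = -2.03 at every visit while all are observed, and it drifts to -2.18 by Week 104. A display in entrants therefore removes the step at entry but starts 0.53 points from the true -1.50 and still drifts by 0.15.
- The earlier visits of those who left do carry the missing information. Weighting the Week 104 values by the original 40/60 split gives 0.4 x (-3.0) + 0.6 x (-0.5) = -1.50. A repeated-measures model uses that information under a missing-at-random assumption.

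**The case against.** **The drift is conditional.** A reader might infer that these curves will improve. The SAP gives no retention or uptake figures, and equal or reverse attrition produces no gain or a loss. This stands: the claim can only be that the curves can move for the wrong reason.

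**The response rates are covered.** A reader might extend the criticism to the as-observed proportions. Section 4.8.3.1 pairs each with an NRI rate at the same visit, and a wide gap between the two would itself show the selection. Symptomatic response and remission use the same two subscores as the contested means. This stands too, and confines the gap to the continuous scores. NRI is not a neutral benchmark at Week 104, however. Anyone who declines the Extension has no data and counts as a non-responder, so the rate falls from 40% to 20.4% even with equal attrition. Nor does the SAP say that the proportion plots are as observed; it leaves that open.

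**Other variables.** hs-CRP, fecal calprotectin and IBDQ are summarised only to Week 52 (section 4.8.3.2), so Extension entry cannot affect them.

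**Attrition is visible elsewhere.** Section 4.1 reports discontinuations with reasons and completers who do not enter the Extension, and section 4 makes n a default statistic for continuous summaries. This helps, but nothing requires n on the plots, and disposition counts do not correct a mean.

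**It is exploratory.** True. No success criterion or multiplicity-controlled test is touched. That limits the weight of the point without removing it.

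**Conclusion.** The point holds for the stool frequency subscore, the rectal bleeding subscore and Partial mMCS. Their by-visit means and plots to Week 104 rest on a shrinking, reselected group with no companion analysis, and the one-visit re-allocation rule does not cure this.

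Direction and size depend on attrition that the SAP does not specify. Under the assumptions shown, a constant true mean change of -1.50 would appear at Week 104 as anything from -1.35 (reverse) through -1.50 (equal) to -2.57 (strong selection). These are illustrations, not forecasts.

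The documents do not support a claim that the curves will improve, that the binary rates lack protection, or that any formal conclusion is at risk. This is a cheap improvement to exploratory reporting.

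**What to change.** Keep the observed-case summaries and make these additions to the SAP:

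- **Section 4.8.3.4, model-based companion.** For the three scores, add an MMRM estimate by visit over all FAS participants in each active-start group. For the placebo-start group, use those continuing to Maintenance, with the maintenance baseline (section 2.1.2) and visits after Week 12 only, in line with section 4.8.
- **104-week analysis, supportive display.** Show the same scores by visit in Extension entrants, the subset already used for TEAEs in section 4.9.1. Label the display as conditional on entry and still subject to later dropout. The placebo-start group keeps its own baseline and visits.
- **Plots.** Print the number observed under each time point.
- **Section 4.8.3.1.** State whether the proportion plots show the NRI approach, the as-observed approach or both.

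The cost is SAP wording and a little extra analysis on data already planned for collection. Two limits should be stated with the results: the MMRM assumes data missing at random, and the Extension-entrant curve applies to entrants only.
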